The basis for dose selection: According to the "Guidance Principles for Estimating the Maximum Recommended Starting Dose for First-in-Human Clinical Trials of Healthy Adult Volunteers" issued by the NMPA, and with reference to the Maximum Recommended Starting Dose (MRSD) for anticancer drugs in ICH S9 "Nonclinical Evaluation for Anticancer Pharmaceuticals", the design of the dosage regimen depends on the data from the long-term toxicity studies of CNSI-Fe in animals. In the toxicity study with 2 intramuscular injections on Day 1 and Day 4, followed by a 4-week recovery period in rats, the Highest Non-Severely Toxic Dose (HNSTD) was 20 mg/kg (calculated as Fe²⁺), corresponding to a Human Equivalent Dose (HED) of 3.6 mg/kg; in the toxicity study with Beagle dogs, the HNSTD was 15 mg/kg, corresponding to an HED of 8.7 mg/kg. Assuming an adult body weight of 60 kg and a safety factor of 6, the MRSD for humans is estimated to be approximately 0.6

mg/kg and 1.45 mg/kg, respectively.

Considering the effective doses in preclinical studies, in multiple solid tumor xenograft models (human colon cancer COLO 205, human breast cancer MDA-MB-231, human breast cancer HCC1954, and human colon cancer HT-29 cells), CNSI-Fe (calculated as Fe²⁺, 0.1875 mg, 0.375 mg, 0.50 mg, 0.75 mg, administered twice on Day 1 and Day 4) significantly inhibited tumor growth. The effective dose and the maximum effective dose were 0.1875 mg and 0.75 mg, respectively. Assuming a mouse body weight of 20 g and an adult human body weight of 60 kg, the corresponding human equivalent doses are 0.84 mg/kg and 3.36 mg/kg, respectively.

Considering the above factors and the safety of the first-in-human trial, this study selected 0.5 mg/kg as the starting dose, with escalating doses of 0.5 mg/kg, 1.0 mg/kg, and 1.5 mg/kg. Calculated based on an average human body weight of 60 kg, the escalating doses are 30 mg, 60 mg, and 90 mg (calculated as Fe²⁺). If ≥2 subjects experience DLT at the 90 mg dose, the dose will be reduced to 75 mg for safety and tolerability observation; if the dose escalation to 90 mg does not reach the MTD, the SRC will discuss whether to further escalate the dose to 120 mg, 150 mg, or even higher, based on the available safety, PK/PD, and preliminary efficacy data (if 120 mg still does not reach the MTD, the SRC will discuss whether to stop the dose escalation or directly proceed to 150 mg or even higher doses).

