The DLT (Dose-Limiting Toxicity) evaluation period is in the first cycle, i.e., within 21 days after the first dose. This stage is tentatively set with 3 dose groups (calculated as Fe^{2+} , 30 mg, 60 mg, 90 mg). If ≥ 2 subjects in the 90 mg group observe DLT, the dose will be reduced to 75 mg for safety and tolerability observation; if the dose is increased to 90 mg and MTD (Maximum Tolerated Dose) is still not reached, the SRC

(Safety Review Committee) will discuss continuing to escalate the dose to 120 mg, 150 mg, or even higher (if MTD is still not reached at 120 mg, the SRC will discuss whether to stop dose escalation or directly proceed to 150 mg or even higher doses).

After 3-6 subjects in each dose group have completed the DLT evaluation, the SRC will evaluate the overall safety of each dose group based on the data obtained and determine whether to continue escalating to the next dose group or to determine the recommended dose for subsequent clinical development.

Enrollment Interval: To fully protect the safety of the subjects, during the dose escalation process, the first subject in each dose group must be dosed at least 3 days after the first dose, and the remaining subjects in that dose group can then start the first dose. The interval for subsequent subjects in the same dose group can be controlled at the discretion of the investigator. The last subject in each dose group must complete the DLT evaluation, and the safety and tolerability must be reviewed by the SRC before the first subject in the next dose group can receive the first dose.

Subject Replacement: During the DLT evaluation period, if a subject is unable to be evaluated for DLT (e.g., the subject's dose of the study drug did not reach at least 80% of the protocol-specified dose, or the subject discontinued study treatment before completing the DLT evaluation period for reasons other than DLT), additional subjects will need to be enrolled to make up the corresponding number in that dose

group.

DLT Definition: This study will grade toxicities according to NCI CTCAE v5.0. DLT refers to the following toxicity reactions that are considered by the investigator and/or the sponsor to be definitely or possibly related to the study drug CNSI-Fe, occurring within the first cycle (i.e., within 21 days after the first dose):

Hematological toxicity:

- (1) Any grade 4 hematological toxicity;

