Before the first CNSI-Fe dose, within 21 days after the first CNSI-Fe dose (specific time points to be determined based on clinical practice).

Subject to the subject's willingness, try to collect tumor tissue samples from the injected lesion before and after the first CNSI-Fe dose; the pre-dose tumor tissue sample can be the most recent archived sample or the sample collected during the screening period; post-dose tumor tissue samples will be collected according to clinical practice as much as possible to complete the tumor PK study (not a mandatory requirement).

Statistical Analysis: Analysis of the Data Set

Full Analysis Set (FAS)

The FAS includes all enrolled subjects who received at least one dose of the study drug and had a measurable lesion at baseline.

Dose-Limiting Toxicity (DLT) Analysis Set (DLTS)

The DLTS includes subjects who completed the DLT evaluation period as per the protocol (defined as receiving at least one dose of the study drug at $\geq 80\%$ of the protocol-specified dose and did not prematurely discontinue or experience a DLT during the DLT evaluation period).

Safety Analysis Set (SS)

The SS includes all subjects who received at least one dose of the study drug and had at least one post-dose safety assessment.

Pharmacokinetic (PK) Analysis Set (PKS)

The PKS includes all subjects who received at least one dose of the study drug and had at least one valid PK measurement.

Pharmacodynamic (PD) Analysis Set (PDS)

The PDS includes all subjects who received at least one dose of the study drug and had at least one valid PD endpoint measurement.

Statistical Analysis Methods

The Statistical Analysis Plan (SAP) will provide detailed specifications and descriptions of all planned statistical analyses in accordance with the protocol, and will be finalized prior to database lock.

The statistical analyses will include demographic and baseline characteristics, safety and tolerability, PK, PD, and efficacy.

The analyses will be primarily descriptive, without formal statistical hypothesis testing.

The statistical analyses will be performed using SAS® version 9.4 or higher.

The following descriptive statistical analyses will be conducted based on the nature of the variables:

Continuous variables: number of non-missing observations, mean and standard deviation (SD), median, minimum, and maximum.

Categorical variables: frequency and percentage.

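### At the conditional 75 mg and 150 mg levels, the inclusive 80% delivery floor for DLT evaluability equals the next lower dose level, so a subject given only that lower dose can help clear the higher one.

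*Combined protocol and SAP*

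**What the plan says.** Under Dose Escalation, the Subject Replacement paragraph gives, as an example of a subject who cannot be evaluated for DLT, one whose dose "did not reach at least 80% of the protocol-specified dose". A subject at exactly 80% is therefore evaluable. Under Statistical Analysis, the DLT Analysis Set repeats the floor: at least one dose at 80% or more "of the protocol-specified dose and did not prematurely discontinue or experience a DLT".

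The basis for dose selection sets the ladder: "the escalating doses are 30 mg, 60 mg, and 90 mg". Further levels are conditional:

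- After two or more DLTs at 90 mg, "the dose will be reduced to 75 mg for safety and tolerability observation".
- If the MTD is not reached at 90 mg, "the SRC will discuss whether to further escalate the dose to 120 mg, 150 mg, or even higher".

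The Study Design and Dosing Volume paragraphs foresee that the full dose may not fit in one lesion, and allow other lesions to be injected at the same time. The inclusion criteria require only one measurable lesion and an injectable lesion. The text available contains no rule for counting a subject by the dose actually received.

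**The concern.** A 3+3 design decides on three to six subjects per level, so each subject counted as DLT-free carries real weight. The evaluability floor is meant to ensure that such a subject was exposed to roughly the dose being judged. If the floor sits at or below the next lower level, it no longer does so: the subject has supplied information about the lower dose, already passed, and is credited to the higher one.

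The affected levels are ones where the trial's main answer could be declared. The 75 mg level is opened to look for a tolerable dose after 90 mg has failed, and 150 mg is the highest level named. The primary objective is the MTD or the maximum injectable dose in humans. Crediting 150 mg to a subject who received 120 mg would misstate either quantity, and the maximum injectable dose most directly.

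**Working it through.** **Inputs.** Per-kg doses and body weight come from the basis for dose selection; the 80% floor from Subject Replacement and the DLT Analysis Set; the conditional levels from the basis for dose selection and Dose Escalation; the escalation rule from Dose Escalation (pass on 0/3, or on at most 1/6).

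**The plan's own ladder.** 0.5, 1.0 and 1.5 mg/kg × 60 kg = 30, 60 and 90 mg. This reproduces.

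**Does the lower level meet the floor of the higher one?** The lower level counts if lower ÷ higher ≥ 0.80.

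| Lower → higher (mg) | Floor = 0.8 × higher (mg) | Lower ÷ higher | Lower dose counts? |
|---|---|---|---|
| 30 → 60 | 48 | 0.500 | No |
| 60 → 90 | 72 | 0.667 | No |
| 90 → 120 | 96 | 0.750 | No |
| 60 → 75 | 60 | 0.800 | Yes, exact tie |
| 120 → 150 | 120 | 0.800 | Yes, exact tie |
| 150 → 180 (assumed step) | 144 | 0.833 | Yes |

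The plan does not name levels above 150 mg. If 30 mg steps continue (assumption), a lower level L counts at L + 30 when L ≥ 0.8(L + 30), that is 0.2L ≥ 24, so L ≥ 120 mg.

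**Size.** With a common DLT risk p, the chance that a level passes is P = (1 − p)³ + 3p(1 − p)⁵. The documents give no DLT risks, so assume 20% at 120 mg and 35% at 150 mg.

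- All at 150 mg: 0.65³ + 3 × 0.35 × 0.65⁵ = 0.2746 + 0.1218 = 0.396.
- One of the first three at 120 mg, everyone else at 150 mg:
  - no DLT in the first three: 0.80 × 0.65² = 0.338;
  - exactly one DLT: 0.20 × 0.65² + 0.80 × 2 × 0.35 × 0.65 = 0.0845 + 0.3640 = 0.4485;
  - P = 0.338 + 0.4485 × 0.65³ = 0.338 + 0.1232 = 0.461.
- All subjects, including any second three, at 120 mg: 0.80³ + 3 × 0.20 × 0.80⁵ = 0.512 + 0.1966 = 0.709.

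**Other assumed risks at the higher level, with 20% at the lower:**

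| Risk at higher level | Full delivery | One of first three at lower dose | All of first three at lower dose | All subjects at lower dose |
|---|---|---|---|---|
| 30% | 0.494 | 0.541 | 0.644 | 0.709 |
| 35% | 0.396 | 0.461 | 0.617 | 0.709 |
| 40% | 0.309 | 0.386 | 0.595 | 0.709 |

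One under-delivered subject thus raises the pass probability by 0.047, 0.065 or 0.077. The direction is upward whenever DLT risk rises with dose.

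**The case against.** The strongest reply is that the floor works where the plan is firm. A reader might infer from the ties that 80% is too loose along the whole ladder. The documents do not support that: 30/60, 60/90 and 90/120 mg are all separated. Nor can the 90 mg floor of 72 mg, which lies below 75 mg, let anyone clear 90 mg wrongly, because 75 mg opens only after 90 mg has failed. One might also object that some floors lie nearer to the lower level than to the higher (96 mg is nearer to 90 than to 120), but nothing in the plan sets a midpoint standard. All of this stands, and it confines the point to 75 mg, 150 mg and possible higher levels.

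Second, the plan offers safeguards. Other lesions can be injected to complete the dose; the 80% criterion in Subject Replacement is given only as an example; and the safety review committee (SRC) reviews each group before escalation. These help in part. A subject with a single injectable lesion is eligible and has no second lesion to use. The DLT Analysis Set states 80% outright, not as an example. Committee review does not change who counts as evaluable, and the text does not require that delivered mg be shown to the committee.

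Third, at 75 and 150 mg the coincidence is exact only for delivery right at the floor, and no under-delivery rate is given. That is fair. The investigational product table lists ferrous sulfate at 30 mg per vial, so one vial short of 150 mg would be exactly 120 mg, and two whole vials without the half would be 60 mg in the 75 mg cohort. This makes the tie plausible, but the documents do not say that shortfalls occur in whole vials.

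**Conclusion.** The point holds in a limited form. Followed exactly, the rule counts a DLT-free subject who received 60 mg towards clearing 75 mg, and one who received 120 mg towards clearing 150 mg. If levels above 150 mg continue in 30 mg steps, the floor falls below the lower level.

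The ties are arithmetic and need no assumption. The direction of the effect assumes that DLT risk rises with dose. Its size rests on assumed risks: about 0.05 to 0.08 on the pass probability for one under-delivered subject, within the range tried. The 0.71 should not be read as an expected result, since it needs every subject in the cohort to receive only the lower dose. Nor do the documents show that incomplete injection is most frequent at the top levels; that is plausible but has no figure behind it.

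Severity is minor to moderate: the affected levels are conditional, but an MTD or maximum injectable dose could be declared there. The available text breaks off in the tumour assessment note to the flow diagram, so a later rule on crediting delivered dose cannot be excluded.

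**What to change.** Before 75 mg, 150 mg or any higher level opens, amend the evaluability rule in both Subject Replacement and the DLT Analysis Set:

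- A DLT-free subject counts at a level only if the delivered dose is at least 80% of it and also clearly above the next lower level studied. One way is a 90% floor at these levels: 0.9 × 75 = 67.5 mg (against 60) and 0.9 × 150 = 135 mg (against 120). With 30 mg steps above that, 0.9(L + 30) exceeds L as long as L is below 270 mg. Changing the wording to strictly more than 80% would remove the two exact ties but would still admit doses just above the lower level, and would not separate 150 from 180 mg.
- Leave the floors at 30, 60, 90 and 120 mg as they are.
- Count every DLT at the assigned level; the tighter floor applies only to DLT-free subjects. Say this explicitly, since the DLT Analysis Set wording can be read as leaving out subjects who had a DLT.
- List delivered mg for each DLT-evaluable subject in the data given to the SRC.

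No planned dose changes. The cost is a short amendment, one listing and an occasional extra replacement at the conditional levels. Replacements must fit within the cap of 30 subjects. Six subjects at each of 30, 60, 90, 120 and 150 mg would already use 5 × 6 = 30, so there is room only if some levels pass with three; the path through 90 mg to 75 mg uses at most 4 × 6 = 24 evaluable subjects.

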**A Phase I Clinical Study Evaluating the Safety, Tolerability, Pharmacokinetic
(PK) Characteristics, and Preliminary Efficacy of Intratumoral Injection of
Ferrous Ion Adsorbed Carbon Nanoparticle Suspension Injection (CNSI-Fe) in
Patients with Advanced Solid Tumors**

Study Protocol

NCT06048367

Version/Date: V3.1/March 28, 2024

Protocol Number: YR-2021-01-CNSI-Fe

Screening Number:

Investigator: [name]

Clinical Trial Institution: West China Hospital, Sichuan University

Trial Site Address: [name]

Sponsor: Sichuan Enray Pharmaceutical Technology Company

Study Protocol

Indication: Patients with advanced solid tumors, such as colorectal cancer, pancreatic cancer, breast cancer, gastric cancer, cervical cancer, lung cancer, head and neck cancer, cholangiocarcinoma, renal cancer, prostate cancer, vulvar cancer, etc., who have failed standard treatment (disease progression after treatment or unable to tolerate treatment) or have no standard treatment available.

Study Objectives

Primary Objectives: To evaluate the safety and tolerability of intratumoral injection of different doses of the ferrous iron adsorbed carbon nanoparticle suspension injection (CNSI-Fe) in patients with advanced solid tumors, and to observe the dose-limiting toxicity (DLT) of CNSI-Fe, and to determine the maximum tolerated dose (MTD) or the maximum injectable dose in humans, which will provide a basis for the selection of doses in subsequent clinical studies.

Secondary Objectives: To evaluate the pharmacokinetic (PK) characteristics of intratumoral injection of different doses of CNSI-Fe in patients with advanced solid tumors;

To preliminarily evaluate the efficacy of intratumoral injection of different doses of CNSI-Fe in patients with advanced solid tumors.

Exploratory Objectives: To evaluate the intratumoral pharmacodynamic (PD)

characteristics of intratumoral injection of different doses of CNSI-Fe in patients with advanced solid tumors (not mandatory);

To evaluate the intratumoral PK characteristics of intratumoral injection of different doses of CNSI-Fe in patients with advanced solid tumors (not mandatory);

To explore the relationship between tumor size and CNSI-Fe injection dose, as well as the dose-effect relationship of CNSI-Fe concentration, in patients with advanced solid tumors receiving intratumoral injection of CNSI-Fe (not mandatory).

Study Endpoints

Primary Endpoints:

Safety

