This study will enroll patients with advanced solid tumors and use the traditional "3+3 method" for dose escalation. The dose escalation principle is: in any dose cohort, 3 subjects will be enrolled first. If none of the first 3 subjects experience DLT during the DLT evaluation period, the next dose cohort can be entered. If ≥ 2 of the first 3 subjects experience DLT during the DLT evaluation period, dose escalation will be stopped (for the 30 mg cohort, if 2 DLTs occur, the sponsor and investigator will jointly decide whether to reduce the dose and continue exploration). If 1 of the first 3 subjects experiences DLT during the DLT evaluation period, an additional 3 subjects will be enrolled in that dose cohort, and if ≤ 1 of the 6 subjects in that dose cohort experience DLT during the DLT evaluation period, the next dose cohort can be entered; if ≥ 2 of the 6 subjects in that dose cohort experience DLT during the DLT

evaluation period, dose escalation will be stopped. The dose prior to the dose at which $\geq 2/3$ or $\geq 2/6$ subjects experience DLT during the DLT evaluation period will be determined as the MTD (if only 3 subjects are enrolled in a cohort, an additional 3 subjects will need to be enrolled).

The “3+3” dose escalation principle

The number of subjects who experienced a dose-limiting toxicity (DLT) within a particular dose cohort	dose escalation principle
0/3	no DLT is observed in the 3 newly enrolled subjects
0/3	no DLT is observed in the 3 newly enrolled subjects
$\geq 2/3$	Dose escalation should be stopped, and that dose will be considered the Maximum Administered Dose (MAD). If the previous lower dose was only administered to 3 subjects, then 3 more subjects need to be enrolled
1/3	
If the 3 newly enrolled subjects in the dose group do not experience a DLT (Dose-Limiting Toxicity), then the study will proceed to the next dose group.
 
 ● ● If ≥ 1 of the 3 newly enrolled subjects in the dose group experience a DLT, then dose escalation will be stopped, and that dose level will be considered the MAD (Maximum Administered Dose). The previous dose level will be considered the MTD (Maximum Tolerated Dose) (if the dose group only had 3 subjects, then an additional 3 subjects will need to be enrolled).

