Adverse Events (AEs): Only serious adverse events (SAEs) related to the protocol-specified procedures should be reported before the start of study drug treatment. After the start of study treatment, all AEs should be reported, regardless of their relationship to the study drug, until 28 days after the last dose. The investigator should follow up on all AEs until the event resolves to baseline or better, is considered stable by the investigator, the subject is lost to follow-up, or the subject withdraws consent. For all SAEs related to the investigational product or study procedures, every effort should be made to follow up until a final outcome can be reported.

Blood routine: Red blood cell count (RBC), hemoglobin (Hb), hematocrit, white blood cell count (WBC) and differential count (neutrophils, eosinophils, lymphocytes, monocytes, basophils and others) and platelet count (PLT). To be performed within 7

days prior to first dose of study drug in the screening period, on Day 7, Day 14, Day 21 of each cycle, at the End of Treatment (EOT) visit, and at the safety follow-up visit (excluding telephone visits). Additional blood routine tests can be performed as needed based on the investigator's clinical judgment.

Urinalysis: Urine specific gravity, urine pH, urine glucose, urine protein, urine ketone, urine red blood cells and urine white blood cells. To be performed within 7 days prior to first dose of study drug in the screening period, on Day 7, Day 14, Day 21 of each cycle, at the EOT visit, and at the safety follow-up visit (excluding telephone visits).

Biochemistry: Glucose, blood urea nitrogen (BUN) or urea, creatinine (Cr), sodium, potassium, magnesium, chloride, calcium, phosphorus, total bilirubin (TBIL), alanine aminotransferase (ALT), aspartate aminotransferase (AST), alkaline phosphatase (ALP), lactate dehydrogenase (LDH), total protein, albumin, triglycerides, total cholesterol, amylase, lipase. To be performed within 7 days prior to first dose of study drug in the screening period, on Day 7, Day 14, Day 21 of each cycle, at the EOT visit, and at the safety follow-up visit (excluding telephone visits). Additional biochemistry tests can be performed as needed based on the investigator's clinical judgment.

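### A DLT that stops the injection below 80% of the dose can be replaced out of the 3+3 count, and the plan does not say whether purely procedural toxicity can be a DLT

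*Combined protocol and SAP*

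**What the plan says.** All references are to the protocol synopsis and the notes to Table 1-1.

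- **DLT Definition.** The toxicity must occur within 21 days of the first dose, meet a listed criterion, and be "considered by the investigator and/or the sponsor to be definitely or possibly related to the study drug CNSI-Fe". One criterion is a catch-all for toxicities of other grades that the investigator and sponsor agree call for ending CNSI-Fe early. The injection procedure is not mentioned.
- **Subject Replacement.** Subjects who cannot be evaluated for DLT are replaced. Two examples are given. One concerns under-dosing: "the subject's dose of the study drug did not reach at least 80% of the protocol-specified dose". The other concerns stopping early: "the subject discontinued study treatment before completing the DLT evaluation period for reasons other than DLT". Only the second excepts DLT.
- **DLT Analysis Set (DLTS).** Members must have received at least 80% of the planned dose and must be subjects who "did not prematurely discontinue or experience a DLT during the DLT evaluation period".
- **Dose Escalation.** "If none of the first 3 subjects experience DLT during the DLT evaluation period, the next dose cohort can be entered". One DLT in three brings three more subjects. At most one in six permits the next cohort; two or more stop escalation. No dose threshold appears in this rule.
- **Primary Objectives.** The trial is "to determine the maximum tolerated dose (MTD) or the maximum injectable dose in humans".
- **Table 1-1 note on adverse events.** A sentence on how long SAEs are followed names two sources: "For all SAEs related to the investigational product or study procedures".

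**The concern.** Treatment in the DLT window is tentatively one intratumoral injection on Day 1. An acute reaction during that injection is an obvious reason for a partial dose. In that case the reason the subject is called not evaluable is the very outcome being counted. Replacing such subjects is informative: it removes an event from the numerator and its subject from the denominator, and puts in someone who tolerated the injection.

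DLT incidence is a primary endpoint, and the MTD follows from the DLT count. A count that loses events makes a dose look better tolerated than it was, and later subjects may then be exposed to a higher one.

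There is also a smaller gap. The objective covers the largest dose that can be injected, but the DLT definition is silent on toxicity judged to come only from the act of injecting.

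**Working it through.** **1. The rules side by side, read literally**

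| Subject in cycle 1 | Subject Replacement | DLTS | 3+3 rule |
|---|---|---|---|
| At least 80% of dose, DLT, stops because of it | Not replaced (DLT excepted) | Excluded as worded | Counted |
| Below 80% of dose, no DLT | Replaced | Excluded | Not counted |
| Below 80% of dose, meets a DLT criterion | Replaced (no exception) | Excluded, on dose and on DLT | Not settled: the event is a DLT, but the subject is replaced |

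The third row is the problem. The DLTS does not resolve it. As worded, that set also leaves out full-dose subjects who have a DLT, which is presumably a drafting slip.

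**2. A worked cohort**

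Five subjects are treated. Two have the injection stopped below 80% by a toxicity meeting a DLT criterion; the other three complete without a DLT.

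- With replacement, the count is 0/3 and the next cohort can be entered.
- With both events counted, escalation stops. The cohort closes with the third clean subject, so both events lie among the first four subjects and at least one among the first three. Either 2 of the first 3 have a DLT, or 1 of 3 does and the fourth subject supplies the second event, giving at least 2 of 6.

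**3. Size, on assumed rates**

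The plan gives no operating characteristics to reproduce. Its only design figure is up to 30 subjects. This equals 6 subjects × 5 named levels (30, 60, 90, 120, 150 mg) = 30, although the plan does not state that derivation. The point does not rest on it.

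Let p be the true DLT risk at a dose. The count permits escalation with probability

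P = (1−p)³ + 3p(1−p)² × (1−p)³.

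- p = 0.33: 0.67³ + 0.99 × 0.67⁵ = 0.301 + 0.134 = 0.43
- p = 0.50: 0.50³ + 1.50 × 0.50⁵ = 0.125 + 0.047 = 0.17

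Let f be the share of DLTs that come with a dose below 80%, each such subject being replaced. A treated subject then has an observed DLT with probability p(1−f) and is lost with probability pf. The risk among those left in the count is

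p′ = p(1−f) / (1−pf),

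which replaces p in the formula for P.

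| p | f | p′ | P |
|---|---|---|---|
| 0.33 | 0 | 0.33 | 0.43 |
| 0.33 | 0.25 | 0.2475/0.9175 = 0.270 | 0.56 |
| 0.33 | 0.50 | 0.165/0.835 = 0.198 | 0.71 |
| 0.50 | 0 | 0.50 | 0.17 |
| 0.50 | 0.25 | 0.375/0.875 = 0.429 | 0.26 |
| 0.50 | 0.50 | 0.25/0.75 = 0.333 | 0.43 |

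Both p and f are assumptions; neither is in the documents. Whenever f is above zero, p′ is below p, so the direction is always towards escalation.

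**The case against.** **The 80% clause is only an example.** Replacement applies to subjects who cannot be evaluated, and a subject with an observed DLT arguably has been. The escalation rule counts subjects who experience a DLT and sets no dose threshold. The catch-all criterion could also make a treatment-ending acute reaction a DLT. This is a fair account of what was probably meant. But the next clause shows that a DLT exception was written where one was wanted, and the DLTS imposes the 80% condition independently. The catch-all can classify an event as a DLT; it does not say that a DLT overrides replacement.

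**Other safeguards exist.** The safety review committee (SRC) reviews the overall safety of each dose group before the next is opened. The trial is suspended for any death not due to progression within 21 days of injection, and when multiple subjects discontinue for reasons other than progression. This stands: the count permits escalation and does not compel it. None of these provisions puts the lost event into the count.

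**A stronger reading that does not stand.** A reader might infer that bleeding, perforation or embolism after injection will be labelled procedural and so fall outside the DLT count, even at grade 4 or 5. The documents do not support that:

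- Possible relatedness in the view of the investigator and/or the sponsor is a low bar, and few events soon after injection would clearly fail it.
- The sentence naming product and procedures concerns SAE follow-up. It is not a causality scheme, and it does not make the two exclusive.
- A fatal procedural event suspends the trial whatever its attribution.
- Nothing in the text links procedural risk to the iron dose; injection volume is set by lesion size.
- Whether purely technical complications should count as DLTs is a debatable clinical rule.

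What remains is that the plan does not say how such events are treated. Nor should much be made of the discontinuation clause: with one injection tentatively planned in the window, a fully dosed subject normally has no further dose to discontinue.

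**Conclusion.** The 80% point holds as a defect of wording with a real consequence. Subject Replacement, the DLTS and the escalation rule do not settle whether a DLT after a partial dose is counted, and the literal text removes it. The bias runs one way, towards calling a dose tolerated. It need not be small: in the worked cohort it turns a stop into 0/3.

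The probabilities are illustrations. They assume independent subjects, a common risk, and replacement of every affected subject, and they leave out the SRC. A share f of a quarter or a half may be high, since only toxicity that interrupts the injection counts towards it; a smaller share gives a smaller shift. They should not be read as the chance that the trial will in fact escalate.

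On procedural toxicity the conclusion is narrower: the DLT definition is silent while the primary objective includes the maximum injectable dose, and the two need reconciling. The available text ends within the tumour-assessment note to Table 1-1, so any fuller rules later in the protocol could not be checked.

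**What to change.** 1. In Subject Replacement, limit the under-dosing clause to subjects who received less than 80% of the planned dose *and had no DLT*.
2. Reword the DLTS so that it contains every dosed subject with a DLT, whatever fraction of the dose was given, together with subjects who received at least 80% and completed the evaluation period without one.
3. Reconcile the DLT Definition with the Primary Objectives by stating whether toxicity judged due only to the injection procedure can be a DLT. Which rule to adopt is a clinical decision and is not proposed here.
4. For each SRC review, tabulate limiting administration-related events and replaced subjects by dose group.

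The cost is a few sentences in an amendment and one extra table column. The downside is that a cohort will occasionally be expanded or stopped by a DLT that followed a partial dose. The grade and duration thresholds, the dose levels and the 3+3 rule itself do not change.
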